## 15.3 APPENDIX C: NUMERIC RATING SCALES (0-10) FOR ORAL PAIN, SENSITIVITY, AND DRYNESS

#### **ORAL PAIN**

#### On a 0 to 10 scale, how PAINFUL is your mouth now? Please circle the number.

0	1	2	3	4	5	6	7	8	9	10	
No pain										Wors	t pain

#### **ORAL SENSITIVITY**

#### On a 0 to 10 scale, how SENSITIVE is your mouth now? Please circle the number.

	0	1	2	3	4	5	6	7	8	9	10
No sens sensitiv											Worst

#### **ORAL DRYNESS**

#### On a 0 to 10 scale, how DRY is your mouth NOW? Please circle the number.

0	1	2	3	4	5	6	7	8	9	10	

No dryness

Worst dryness

## **15.4** APPENDIX D: GLOBAL SCALE

Compared to TWO WEEKS ago, what is the overall condition of your mouth? Please circle.

Much worse	A little worse	Same	A little better	Much better

#### **15.5** APPENDIX E: PAINOMETER (POM) ASSESSMENT SHEET

	D (	, ,	T .•		
Baseline	Date:	_//	Time:	Subject Study Number:	

# I INSTRUCTIONS: Ask the participant to choose words from the Sensory pain intensity list and the Affective pain intensity list below to describe present oral pain- Circle the chosen letter/word and number/word from the lists.

SEI	NSORY	AF	FECTIVE
А	Cramping	1.	Nagging
В.	Dull	2.	Agonizing
С.	Splitting	3.	Annoying
D.	Burning	4.	Troublesome
E.	Sore	5.	Killing
F.	Shooting	6.	Tiring
G.	Radiating	7.	Unbearable
Н.	Hurting	8.	Sickening
I.	Crushing	9.	Terrifying
J.	Aching	10.	Miserable
Κ.	Stabbing	11.	Torturing
L.	Sharp		
М.	Tearing		
N.	Pressing		

**II. INSTRUCTIONS:** Ask the participant to choose the word which describes the duration of oral pain and check the response:

Continuous

Periodic (Comes and goes)

III. INSTRUCTIONS: Ask the participant to choose words from the Sensory pain intensity list and the Affective pain intensity list below to describe present oral pain with swallowing Circle the letters/numbers and words chosen from the lists.

SENSORY	AFFECTIVE
A. Cramping	1. Nagging
B. Dull	2. Agonizing
C. Splitting	3. Annoying
D. Burning	4. Troublesome
E. Sore	5. Killing
F. Shooting	6. Tiring
G. Radiating	7. Unbearable
H. Hurting	8. Sickening
I. Crushing	9. Terrifying
J. Aching	10. Miserable
K. Stabbing	11. Torturing
L. Sharp	_
M. Tearing	

N. Pressing

IV. INSTRUCTIONS: Ask the participant to choose the word which describes the duration of oral pain with swallowing and (') the response

Continuous

Periodic (Comes and goes)

#### Scoring of Painometer (POM) Assessment Sheet

Weighted scores for the Painometer sensory word descriptors are:

- A. Cramping = 4
- B. Dull = 1
- C. Splitting = 5
- D. Burning = 4
- E. Sore = 1
- F. Shooting = 5
- G. Radiating = 3
- H. Hurting = 2
- I. Crushing = 4
- J. Aching = 3
- K. Stabbing = 5
- L. Sharp = 5
- M. Tearing = 5
- N. Pressing = 2

Weighted scores for the Painometer affective word descriptors are:

- 1. Nagging = 1
- 2. Agonizing = 4
- 3. Annoying = 1
- 4. Troublesome = 2
- 5. Killing = 5
- 6. Tiring = 3
- 7. Unbearable = 5
- 8. Sickening = 4
- 9. Terrifying = 5
- 10. Miserable = 3
- 11. Torturing = 5

Total score is calculated by simple summation of individual weighted scores.

## 15.6 APPENDIX F: ORAL HEALTH IMPACT PROFILE (OHIP-14)

#	Because of problems with your teeth, denture or mouth have you	Never (0)	Hardly ever (1)	Occasionally (2)	Often (3)	Very Often (4)
1	Had trouble pronouncing words					
2	Felt sense of taste has worsened					
3	Had painful aching in the mouth					
4	Found it uncomfortable to eat any foods					
5	Have been self-conscious					
6	Felt tense					
7	Had an unsatisfactory diet					
8	Had to interrupt meals					
9	Found it difficult to relax					
10	Have been a bit embarrassed					
11	Have been irritable with other people					
12	Had difficulty doing usual jobs					
13	Felt life in general was less satisfying					
14	Have been totally unable to function					

Total \_\_\_\_\_

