## 1.1.2 Secondary Objectives

- 1.1.2.1 To assess the effect of topical clobetasol on oral cGVHD related pain, sensitivity, and dryness.
- 1.1.2.2 To evaluate the basic pharmacodynamics and pharmacokinetics of clobetasol mouth rinse in cGVHD patients.
- 1.1.2.3 To obtain a pilot assessment of patient perceived oral health in cGHVD and its response to treatment with topical clobetasol.
- 1.1.2.4 To evaluate the validity of the NIH Oral cGVHD Clinical Scoring instrument.
- 1.1.2.5 To evaluate the immunological profile present at baseline and after clobetasol treatment in oral tissue to identify potential biomarkers for disease response or resistance to clobetasol.
- 1.1.2.6 To evaluate blood and saliva to identify potential biomarkers for oral cGVHD disease activity and response to topical clobetasol.

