## 3.5.5 Oral Health Impact Profile–14

Oral Health Impact Profile–14 (OHIP-14, **Appendix F**) is a 14 item questionnaire developed to assess the state of oral health as perceived by a patient . Increased use of patient centered outcome measures has been advocated in the recent years. Patient centered outcome measures complement objective measures to provide a more complete picture of the impact of disease and treatment. OHIP-14 has been used in oral disease studies including oral lichen planus (a dermatological condition with manifestation similar to chronic oral GVHD). It has been shown to have high validity and reliability, and to be sensitive to treatment effects.

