## 15.11 APPENDIX K: ORAL HEALTH IMPACT PROFILE (OHIP-14)

Date:	/	/	Timepoint:	LIP print name:	[name]	LIP
Signat	ure:					

#	Ha tenido los siguientes problemas, debido a dificultades con su boca, sus dientes o dientes postizos:	Nunca (0)	Casi nunca (1)	Ocasional- mente (2)	Frecuente- mente (3)	Muy frecuen- te (4)
1	¿Ha tenido dificultad al pronunciar palabras?					
2	¿Se ha empeorado el sentido del gusto ha empeorado?					
3	¿Ha estado adolorida su boca?					
4	¿Se siente incómodo al comer?					
5	¿Se siente muy consciente de sí mismo?					
6	¿Se siente tenso/a?					
7	¿Ha sido insatisfactoria su dieta?					
8	¿Ha tenido que interrumpir tiempos de comida?					
9	¿Se da cuenta que le es muy difícil relajarse?					
10	¿Se siente un poco avergonzado/a?					
11	¿Se ha sentido muy irritable hacia otras personas?					
12	¿Ha tenido dificultad haciendo cosas que usualmente ha hecho sin dificultad?					
13	¿Se siente menos satisfecho/a con su vida en términos generales?					
14	No ha podido funcionar del todo.					

Total \_\_\_\_\_

Protocol 12C0068

English version translation of Appendix J

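### The OHIP-14 forms print no recall period although they are repeated at two-week visits, so day-14 and day-28 scores can include pre-treatment symptoms and understate perceived change by an unknown amount.

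*Combined protocol and SAP*

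**What the plan says.** Secondary objective 1.1.2.3 is "To obtain a pilot assessment of patient perceived oral health in cGHVD and its response to treatment with topical clobetasol". Section 3.5.5 says that OHIP-14 "is a 14 item questionnaire developed to assess the state of oral health as perceived by a patient", and adds: "It has been shown to have high validity and reliability, and to be sensitive to treatment effects". Section 6.3.1 lists OHIP-14 among the scales for the secondary endpoints, beside the patient-reported global scale.

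The English form (Appendix F) heads its 14 items with "Because of problems with your teeth, denture or mouth have you" and scores each from 0 (never) to 4 (very often). The Spanish form (Appendix K) begins "Ha tenido los siguientes problemas, debido a dificultades con su boca, sus dientes o dientes postizos" and uses the same five-step frequency scale. Neither form gives a time frame. Nor do the other legible copies: those bound into Section 3.1, and the English version that follows Appendix K.

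Sections 3.3.1 to 3.3.4 and Appendix G schedule OHIP-14 at baseline, day 14, day 28 and day 56. Patients who start on placebo have two day-14 visits, one at unblinding and one after 14 days of clobetasol. Visits may vary by 2 days either way.

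**The concern.** A frequency answer needs a period to count over. Without one, each patient chooses, and successive scores may cover overlapping stretches of time. A patient who improves soon after starting the rinse, but who answers for the past few months, will report much the same frequency at day 14 as at baseline. The measured change then falls short of the true change by an amount that differs from patient to patient.

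What is at stake is the perceived response to treatment that objective 1.1.2.3 asks for, including the day-14 visit that closes the only blinded placebo comparison. Patients answer the form as printed, so the analyst cannot supply the missing period afterwards.

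The Spanish form adds a smaller problem. Some of its items ask about the present state, as in "Se siente tenso/a", where the English asks what has happened.

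**Working it through.** **1. Is a recall period given anywhere?** I looked at each place that could give one.

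| Place | Time frame |
|---|---|
| OHIP-14, Appendix F and other legible English copies | none |
| OHIP-14 Spanish, Appendix K | none |
| Section 3.5.5 | none |
| Sections 3.3.1 to 3.3.4, Section 10.2, Appendix G | visit dates or no mention; no recall period |
| Numeric scales, Appendix C | now |
| Painometer, Appendix E | present pain |
| Global Scale, Appendix D | "Compared to TWO WEEKS ago, what is the overall condition of your mouth" |

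The stem is the same in the complete English copies, and the Spanish form lacks a period too, so faulty PDF reading is an unlikely cause.

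**2. Is there a plan figure to reproduce?** No. Section 10.2 gives no test, effect size or power for OHIP-14. Its power statements concern OMRS and the biopsy parameters.

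**3. Illustration of the dilution.** The documents give no recall window, so this is assumption throughout. Suppose that answers average evenly over the last R days, that symptoms were constant before treatment, and that the full change comes on the first day of clobetasol. After d days on drug:

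- share of the true change that shows: w = min(d, R)/R
- share of the window that precedes treatment: 1 − w

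| Assumed R (days) | w at d = 14 | w at d = 28 |
|---|---|---|
| 14 | 14/14 = 100% | 100% |
| 28 | 14/28 = 50% | 28/28 = 100% |
| 56 | 14/56 = 25% | 28/56 = 50% |
| 91 | 14/91 = 15% | 28/91 = 31% |
| 365 | 14/365 = 4% | 28/365 = 8% |

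Any window over 14 days brings pre-treatment time into the day-14 score, and any window over 28 days brings it into the day-28 score.

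On the form's own scale, let all 14 items fall from 3 (often) to 1 (hardly ever). The baseline total is 14 × 3 = 42 and the true later total is 14 × 1 = 14. The recorded day-14 total is 14 × [3(1 − w) + w] = 42 − 28w:

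- R = 14: 42 − 28 × 1 = 14
- R = 28: 42 − 28 × 0.5 = 28
- R = 91: 42 − 28 × 0.154 = 38
- R = 365: 42 − 28 × 0.038 = 41

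**4. Patients who start on placebo.** For them d counts from the switch to clobetasol. At 28 days of clobetasol they are 14 + 28 = 42 days past randomization. A window over 28 days reaches into the placebo phase, and one over 42 days reaches before randomization.

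**5. Tense of the Spanish items.** The Spanish stem is in the present perfect. Items 4, 5, 6, 9, 10 and 13 (6 of 14) are in the present tense. The English stem puts all 14 items in the present perfect. The Spanish form therefore mixes time frames and does not match the English.

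**The case against.** **Patients may supply a sensible period themselves.** Several copies of the form carry date and time-point fields, and a patient who repeats the form at each visit may answer for the time since the last one. The dilution would then be absent or small. This stands as a limit on size. It does not remove the gap, because nothing on the form makes patients read it alike. A reader might infer that a patient whose symptoms stopped on day 1 has to answer above *Never* at day 14. That follows only if the question is read as covering all past time, and the documents do not say that patients read it so.

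**OHIP-14 is not alone.** A reader might infer that objective 1.1.2.3 rests on it entirely. The documents do not support this: Section 3.5.4 uses the Global Scale for patients' perception of change, Section 6.3.1 lists it beside OHIP-14, and its form is anchored to two weeks. It is, however, a single item that compares with two weeks before, so at day 28 it does not measure change from the start of clobetasol. OHIP-14 remains the main multi-item measure.

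**Section 3.5.5 cites evidence of sensitivity to treatment.** Whether the cited studies used this stem or this interval cannot be seen from the documents. The statement therefore neither settles the point nor can be called wrong.

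**The language point is small.** The Spanish stem is itself in the present perfect and heads all the items, and a constant offset by language would partly cancel in change from baseline. Section 11.6.2 expects Spanish-speaking participants but gives no number, so the effect cannot be sized.

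**The stakes are limited.** This is a pilot assessment with no test or decision rule attached, and dilution pulls towards no change, so it would not by itself create a false benefit. That is correct.

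**Conclusion.** The omission is real: no legible OHIP-14 form, English or Spanish, and no section of the protocol states a recall period, while the other patient-reported forms for oral symptoms and condition do fix a time. It can dilute the measured OHIP-14 change at day 14 and day 28 and add noise between patients.

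The size is unknown. The range above, from no loss at a 14-day window to 4% of the change showing at day 14 with a 365-day window, rests wholly on an assumed even recall window, constant earlier symptoms and an immediate full change. A reader might take these percentages as an estimate of the bias in this trial, but the documents contain nothing that would support that. The mismatch of tense between languages is a secondary defect of the same kind.

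The OMRS primary endpoint and the power figures in Section 10.2 are not affected. The correction is worth making because it is cheap and because the gap cannot be repaired after the forms are completed.

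**What to change.** Print one fixed recall period, *In the past 2 weeks*, in the stem of every English OHIP-14 form, with *En las últimas 2 semanas* on the Spanish form. Put Spanish items 4, 5, 6, 9, 10 and 13 in the same tense as the English. State in Section 3.5.5 that each score refers to the two weeks before the visit.

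Two limits should be stated with it. Follow-up comes 28 days after the end of treatment, so a two-week window covers only the last half of that interval. A day-14 visit held 2 days early falls on day 12, so the window admits up to 2 pre-treatment days and 12/14 = 86% of it is on treatment. Both are minor beside an open window.

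The cost is one stem line in two languages, six Spanish items and one sentence, with the IRB review that any amendment needs. Totals become slightly less comparable with OHIP-14 studies that used another time frame or the present stem. Forms already collected on the current wording should be flagged in the data, and their undefined recall period reported as a limitation.

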## 15.7 APPENDIX G: SCHEDULE OF EVALUATIONS AND EVENTS

Patients Randomized to Clobetasol Oral Rinse Schedule:

Patient Evaluations and Events	Screening and Baseline (Day -7 to 0 )*	Day 0 *	Interim Evaluation (Day 14) *g	End of Intervention (Day 28)*	Follow-up (Day 56) * (or end of treatment visit)	Follow up (3 months and 6 months post treatment) #
History and Physical Exam t	Xt		Xt	Xt	Xt	Xt
NIH Advanced Directives Form						
cGVHD NIH Organ Staging	X				X	
Clinical Photographs	X		X	X	X	
Urine pregnancy test	X					
Informed Consent	X					
Randomization	X					
CBC, Acute care, mineral and liver panel & LDH, TBNK	X		X	X	X	
Serum Cortisol Level	X		X	X	X	
Research Saliva and Plasma Collection	X		X	X	X	
OMRS	X		X	X	X	
Oral cGVHD Clinical Scoring	X		X	X	X	

Patient Evaluations and Events	Screening and Baseline (Day -7 to 0 )*	Day 0 *	Interim Evaluation (Day 14) *g	End of Intervention (Day 28)*	Follow-up (Day 56) * (or end of treatment visit)	Follow up (3 months and 6 months post treatment) #
Oral HSV by PCR	Х			X		
Oral Pain, Sensitivity, Dryness Scales	Х		X	X	X	
Global Scale			X	X	X	
РОМ	Х		X	X	X	
OHIP-14 (Oral QOL)	Х		X	X	X	
Biopsy/Tissue Collection	Х			Xt		
ACTH Stimulation Test	Х			X	X p	
Adrenocorticotropic Hormone blood level	Х			X	Х	
Hemoglobin A1C level	Х	Х	X	X	X	
Compliance Evaluation			X	X		
Monitoring for Adverse Events			X	X	X	X
Start of intervention		Х				
Completion of the intervention				X		

 $^{*}\pm 2 \ days$ 

tOptional

p Per PI discretion (at day 56 or day 70 visit depending on subject randomization group) if there is concern for endocrine side-effects)

# This follow up can be done in person or via telephone call as per Section **3.7**g Patients initially randomized to 2 weeks of placebo will have two Day 14 Interim Evaluation visits, one at unblinding and one after 14 days of clobetasol therapy.

h As indicated in Section 11.5, all subjects  $\geq$  age 18 will be offered the opportunity to complete an NIH advanced directives form. This should be done preferably at baseline but can be done at any time during the study as long as the capacity to do so is retained. The completion of the form is strongly recommended, but is not required.

Version Date: January 24, 2017

## 15.8 APPENDIX H: DATA COLLECTION ELEMENTS REQUIRED BY PROTOCOL

All of the following elements will be recorded in the research database.

## **Patient Enrollment**

## **Recipient**

- Date of birth, age, sex, race, ethnicity
- Height
- Weight
- Karnofsky Performance Status
- Date of original diagnosis of the underlying disease (month/year)
- Diagnosis for which transplant was performed
- Date and type of transplant
- Conditioning regimen
- Acute GVHD yes/no
- Chronic GVHD date of diagnosis
- Chronic GVHD classification (late, overlap, classic)
- Prior systemic therapy for cGVHD
- Prior oral therapy for cGVHD
- Date of Informed Consent signature, consent version and date of registration
- Optional Baseline History/Physical
- Baseline Symptoms
- Intensity of current immunosuppression: None, Mild (single agent prednisone ≤0.5 mg/kg/day), Moderate (prednisone ≥0.5 mg/kg/day and or any single agent/modality), High (2 or more agents/modalities ±prednisone ≥0.5 mg/kg/day)
- Clinician's impression of activity: Inactive, off systemic therapy or topical immunosuppression; Inactive, on systemic therapy or topical immunosuppression; Active, irrespective of the level of current therapy; Highly Active, irrespective of the level of current therapy
- Findings of consultations done at screening

## Donor

- Age at transplant
- Relationship, sex
- Degree and type of HLA match (allele or serologic)
- CMV status

## Study Drug administration and response for each course of therapy given

- Dates study rinse given
- Actual dose given
- Response assessment (OMRS score) for each visit

## Laboratory and Diagnostic Test Data

- All Clinical laboratory and diagnostic test results done at screening except diagnostic tests which are not specified in the protocol, and if the results are not needed to document the start or end of an adverse event that requires reporting.
- All tests done to document resolution of adverse events
- Serologies-CMV and HSV
- Volume of stimulated and unstimulated saliva at each visit.

## **Adverse Events**

- All unexpected serious adverse events that are possibly, probably, or definitely related to the research
- All deaths, except deaths due to progressive disease
- All Protocol Deviations
- All Unanticipated Problems

## **Concomitant Measures**

- Baseline immunosuppressive medications
- Other therapy for recorded adverse events

## **Off study**

- Date and reason for off study
- Date and cause of death
- Autopsy findings

## 15.9 APPENDIX I: TOPICAL CLOBETASOL 0.05% ORAL RINSE FOR ORAL CHRONIC GRAFT-VERSUS-HOST DISEASE PATIENT DIARY

INSTRUCTIONS: Rinse with the study medication THREE times a day for 2 minutes and spit out. Do not eat, drink or brush your teeth for at least 30 minutes after study medication use.

Rinse with the nystatin suspension ONE time a day for at least 30 seconds after your evening meal. Do not eat, drink or brush your teeth for at least 10 minutes after nystatin use.

You can use painkiller rinse (viscous lidocaine) as needed to relieve oral discomfort. Do not use the painkiller rinse at least 30 minutes before and after using the study rinse or nystatin. Do not use any other mouthwashes, rinses or oral hygiene products except toothpaste.

Record the level of oral pain and oral dryness for the day at its WORST using a number from 0 (no pain/dryness) to 10 (the worst possible pain/dryness).

Day of the week	Date	Time Write down the time you use a dose of study rinse and circle AM or PM. (Remember that you are to use the rinse 3 times per day)	Mouth Pain Rating Rate your pain with the first daily rinse by circling the number on the 0 to 10 pain scale. Zero (0) is no pain and ten (10) is the worst pain	rinse by circling the number on the 0 to 10 pain scale. Zero (0) is no dryness and ten (10) is the worst dryness	Medications for Pain List any medications you have taken for pain in your mouth in the past 24hrs	Side Effects List any side effects that you have experienced in the past 24hrs	Comments Include any additional information such as why you missed/skipped a dose of study rinse
		Dose 1 AM/PM	0 1 2 3 4 5 6 7 8 9 10	0 1 2 3 4 5 6 7 8 9 10			
		Dose 2 AM/PM					
		Nystatin PM					
		Dose 3 AM/PM					
		Dose 1 AM/PM	0 1 2 3 4 5 6 7 8 9 10	0 1 2 3 4 5 6 7 8 9 10			
		Dose 2 AM/PM					
		Nystatin PM					
		Dose 3 AM/PM					
		Dose 1 AM/PM	0 1 2 3 4 5 6 7 8 9 10	0 1 2 3 4 5 6 7 8 9 10			
		Dose 2 AM/PM					
		Nystatin PM					
		Dose 3 AM/PM					
		Dose 1 AM/PM	0 1 2 3 4 5 6 7 8 9 10	0 1 2 3 4 5 6 7 8 9 10			
		Dose 2 AM/PM					
		Nystatin PM					
		Dose 3 AM/PM		0 1 2 3 4 5 6 7 8 9 10			
		Dose 1 AM/PM	0 1 2 3 4 5 6 7 8 9 10	012345078910			
		Dose 2 AM/PM					
		Nystatin PM Dose 3 AM/PM					
		Dose 3 AM/PM Dose 1 AM/PM	0 1 2 3 4 5 6 7 8 9 10	0 1 2 3 4 5 6 7 8 9 10			
		Dose 2 AM/PM	012343078910				
		Nystatin PM					
		Dose 3 AM/PM					
		Dose 3 AM/PM Dose 1 AM/PM	0 1 2 3 4 5 6 7 8 9 10	0 1 2 3 4 5 6 7 8 9 10			
		Dose 1 AM/PM Dose 2 AM/PM	012040078910				
		Nystatin PM					
		Dose 3 AM/PM					
		Dose 5 AM/PM					

Patient Signature: \_\_\_\_\_ Date: \_\_\_\_\_

## **15.10** APPENDIX J: SPANISH LANGUAGE TRANSLATIONS OF THE PATIENT-REPORTED OUTCOME FORMS

	Painor	neter (F			
Date: Signat	//	/	Time:	Timepoint:	LIP: [name] LIP

I INSTRUCCIONES: Pídale al participante que elija palabras de la lista de intensidad del dolor Sensorial tanto como de la lista de intensidad de dolor Afectivo a continuación, para describir el dolor oral en estos momentos. Haga un círculo alrededor de la letra y palabra y del número y palabra de las listas a continuación.

SENSORIAL	AFECTIVO
A Calambre	1. Irritante
B. Leve	2. Agobiante
C. Enloquecedor	3. Fastidioso
D. Ardor	4. Molestoso
E. Adolorido	5. Mortal
F. Punzante	6. Fatigoso
G. Que irradia	7. Insoportable
H. Que duele	8. Deprimente
I. Triturante	9. Espantoso
J. Resentido	10. Miserable
K. Como puñaladas	11. Torturante
O. Agudo	
P. Desgarrante	

Q. Insistente

II. INSTRUCCIONES: Pídale al participante que elija la palabra que describe la duración del dolor oral y marque la respuesta:

Continuo

Periódico (Se viene y se va) \_

III. INSTRUCCIONES: Pídale al participante que elija palabras del listado de intensidad del dolor Sensorial y del dolor Afectivo a continuación, para describir el dolor oral al deglutir. Marque con un círculo las letras/números y los números/palabras de estas listas.

SENSORIAL	AFECTIVO
A Calambre	1. Irritante
B. Leve	2. Agobiante
C. Enloquecedor	3. Fastidioso
D. Ardor	4. Molestoso
E. Adolorido	5. Mortal
F. Punzante	6. Fatigoso
G. Que irradia	7. Insoportable

- H. Que duele 8. Deprimente 9. Espantoso I. Triturante 10. Miserable J. Resentido
- K. Como puñaladas
- L. Agudo M. Desgarrante
- N. Insistente

- 11. Torturante

